13.6. Investigator and Study Staff Requirements

All Investigators must be qualified by training and experience to conduct the proposed research, and must accept responsibility for all research activities at their site.

Prior to study initiation, the Investigator will complete and submit to the Sponsor all documents required by 21 CFR Part 50, 56, and 312, ISO 14155, and/or ICH (E6) (Section 8.0), including financial disclosure information as required. Additionally, each Investigator must assure the study

staff is qualified by training and experienced to assist with the proposed research. This training must be documented and maintained at the study site.

Upon completion or termination of the study, the Investigator will submit a final written report to the IRB/IEC. The Investigator will provide the Sponsor or designee with copies of all IRB/IEC actions regarding the study.

14. DATA MANAGEMENT AND RECORDKEEPING

14.1. Electronic Case Report Forms

Electronic case report forms are created using a validated EDC system. They are to be completed in English for all subjects.

Entered data will be reviewed for consistency and correctness with the protocol. All discrepancies will be forwarded to appropriate EDC users for resolution. An electronic audit trail will be maintained to track all changes to the database.

14.2. Case Report Forms

Electronic Case Report Forms are to be completed for all consented subjects. For subjects who sign the ICF but are subsequent screen failures, no AE or SAE data will be collected after these subjects fail to meet eligibility criteria and do not qualify for randomization.

14.3. External Data

Any data that is collected electronically will be uploaded from the vendor's database to Bellerophon Pulse Technologies database via secure transfer. Details of this process will be coordinated with the vendor and described in a Data Transfer Specifications document.

14.4. Inspection of Records

In compliance with local regulations, US Federal regulations and ICH GCP guidelines, it is required that the Investigator and institution permit authorized representatives of the Sponsor, of the regulatory agency(s), and the IEC direct access to review the subject's original medical records for verification of study-related procedures and data. Direct access includes examining, analyzing, verifying, and reproducing any records and reports that are important to the evaluation of the study. The Investigator is obligated to inform the subject and obtain their consent to permit named representatives to have access to his/her study-related records without violating the confidentiality of the subject.

14.5. Retention of Records/Critical Documents

In compliance with ICH GCPs and applicable regulatory requirements, copies of all records (e.g., informed consent documents, laboratory data slips, source documents, safety reports, test article dispensing records) which support the eCRFs, must be retained in the files of the responsible Investigator for a minimum of 2 years (for EU: records to be retained for 15 years) following notification by Sponsor that all investigations at all sites are completed, terminated, or discontinued. If the Investigator retires, relocates, or for other reasons withdraws from the responsibility of keeping the trial records, custody must be transferred to a person who will accept the responsibility. Bellerophon Pulse Technologies LLC must be notified in writing of the name and address of the new custodian.

15. ETHICS

The study will be conducted in accordance with this protocol, the principles that have their origins in the Declaration of Helsinki, as well as ICH GCP and applicable federal, state, and local regulatory requirements. All essential documents will be archived.

The protocols and local ICFs must be reviewed and approved by each of the participating institutions' IRB/IEC prior to the initiation of subject recruitment. The IRB/IEC must be notified of all subsequent protocol amendments. In addition, progress reports will be submitted to the IRB/IEC by the Investigator as indicated by IRB/IEC's guidelines. Each IRB/IEC must meet the FDA's, and/or European Medicines Agency (EMA), International Conference on Harmonization (ICH), and any additional state and/or national requirements for composition, documentation, and operational procedures.

The Investigator shall provide the Sponsor with the IRB/IEC's written notification of approval along with the IRB/IEC membership list and/or statement that the IRB/IEC operates in accordance with GCP.

15.1. Informed Consent Form(s) for Study Subjects

The informed consent must contain all elements required by the FDA under 21 CFR Part 50 and ICH (E6) (Section 4.8), FDA Guidance for Industry, Investigators, and Institutional Review Boards, on Conduct of Clinical Trials of Medical Products during COVID-19 Public Health Emergency, as well as any other elements required by state, local and institutional policies and applicable ISO standards.

Due to the infectious nature of COVID-19 and subjects in COVID-19 isolation, subjects may provide consent:

- using electronic methods, if such technology is available, or
- if electronic consenting is not available, a standard process should be implemented to obtain subject informed consent, consistently.

A copy of the informed consent document signed by the investigator and witness should be placed in the subject's source documents after the subject has had adequate time to ask questions and consider their participation in the study, with a note by the investigator of how the consent was obtained (eg, telephone call). The study record at the investigational site should document how it was confirmed that the subject signed the consent form (ie, either using attestation by the witness and investigator or the photograph of the signed consent). The note should include a statement of why the informed consent document signed by the subject was not retained (eg, due to potential contamination of the document by infectious material).

Consent must be obtained before any protocol related procedures that are not part of the subject's normal care. The date and time the consent was finalized should be recorded in the subject's medical chart. The subject must receive a copy of a dated, and signed consent form according to ICH GCP guidelines. Subjects will be informed of any significant new finding developed during the course of the research that may affect their decision to continue participation.

Failure to provide informed consent renders the subject ineligible for the study.

15.2. Independent Ethics Committee/Institutional Review Board

15.2.1. Amendments to the Protocol

Neither the Investigator nor the Sponsor will amend nor modify the protocol without written notification of the other. All amendments must be approved by the Sponsor prior to implementation. All amendments must be submitted to the IRB/IEC as required. The IRB/IEC must approve major amendments prior to implementation at the study site except in the case of ensuring subject safety, as required.

16. REPORTS AND PUBLICATIONS

The Sponsor recognizes that the institution and/or Principal Investigator may desire to publish or present information related to the subject matter of the study. No such publication or presentation, including without limitation, any such publication or presentation by an individual Principal Investigator in a multicenter study, may occur without the express written approval of the Sponsor which approval shall not be unreasonably withheld.

In the case of a multicenter study, no individual publication shall be made until after the planned multi-center publication, or 18 months after study completion, whichever shall first occur.

In the event the Institution and/or Principal Investigator desire to make a publication or presentation, the Institution and/or Principal Investigator will provide a copy of the proposed publication or presentation of the study to the Sponsor 90 days prior to submission for publication or presentation in order to ascertain whether public disclosure will adversely affect patent rights, copyrights, or proprietary rights or any other interest of the Sponsor. In the event of objection by the Sponsor, for any reason, the institution and Principal Investigator further agree to delay the publication or presentation until modifications or revisions to the publication or presentation have been made which are mutually satisfactory to the Institution/Principal Investigator and the Sponsor.

This trial will be listed on [clinicaltrials.gov](#).

17. STATISTICAL CONSIDERATIONS

This section provides a general description of the statistical methods to be used in analyzing both safety and efficacy data. The key statistical issues or considerations will be addressed. A more detailed statistical analysis plan will be provided in a separate document that will be finalized before unblinding of treatment assignment.

17.1. Primary Efficacy Analysis:

The primary analysis will be analyzed using a logistic regression model (Agresti, 2007, John Wiley and Sons) with treatment, age, gender and baseline stratification factors (used for stratified randomization) as covariates. Supportive analysis may be carried out while including other baseline subject level and site level covariates as needed (to be specified in the SAP).

The primary analysis is conducted at Day 28, however, we plan to conduct sensitivity analysis at Day 7 and Day 14 and day of discharge.

In addition, where appropriate, we plan to conduct time to event analysis to supplement the proportional analyses.

Details around the analysis plan will be provided in the SAP.

Expected Sample-Size

Initial assessment of the sample size is based on the historical experience of ~30% of hospitalized COVID-19 subjects deteriorating to needing increased respiratory support and the experience in our Emergency Expanded Access that indicates ~15% deteriorate.

Using 30% for the placebo arm and 15% for the iNO arm results in a sample size of 382 for a 1:1 randomized trial with 90% power for one-sided p-value of 0.025.

Based on this analysis, we are targeting a sample size of ~500 subjects. However, we note that the sample size may need to be re-assessed as the data on COVID-19 is rapidly evolving.

17.2. Interim Analysis:

An interim analysis for futility is planned after ~100 subjects have completed assessments through Day 28 in order to assess the failure rate in the iNO group versus placebo for the primary endpoint (death and respiratory failure). The interim analysis will be carried out by an independent external DMC based on pre specified criteria and stopping rules as detailed in the SAP.

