Initial assessment of the sample size is based on the historical experience of ~30% of hospitalized COVID-19 subjects deteriorating to needing increased respiratory support and the experience in our Emergency Expanded Access that indicates ~15% deteriorate.

Using 30% for the placebo arm and 15% for the iNO arm results in a sample size of 382 for a 1:1 randomized trial with 90% power for one-sided p-value of 0.025.

Based on this analysis, we are targeting a sample size of ~500 subjects. However, we note that the sample size may need to be re-assessed as the data on COVID-19 are rapidly evolving.

Interim Analysis:

An interim analysis for futility is planned after ~100 subjects have completed assessments through Day 28 in order to assess the failure rate in the iNO group versus placebo for the primary endpoint (death and respiratory failure). The interim analysis will be carried out by an independent external DMC based on pre specified criteria and stopping rules as detailed in the SAP.

[figure not shown]
Study Diagram:

TABLE OF CONTENTS

1.	STUDY CONTACT INFORMATION	2
2.	SYNOPSIS	4
4.	LIST OF ABBREVIATIONS AND DEFINITIONS OF TERMS.....	17
5.	INTRODUCTION	19
6.	OBJECTIVES.....	21
6.1	Primary Objective.....	21
6.2	Secondary Objective:.....	21
7.	ENDPOINTS	22
7.1.	Primary Endpoint.....	22
7.2.	Secondary Endpoints	22
7.3.	Safety Endpoint	22
7.4.	Overall Study Design.....	22
7.5.	Treatment Assignment.....	23
8.	STUDY POPULATION.....	24
8.1.	Number of Subjects to be Studied	24
8.2.	Inclusion Criteria	24
8.3.	Exclusion Criteria	24
9.	SUBJECT DISCONTINUATION, WITHDRAWAL AND TERMINATION FROM THE STUDY	26
9.1.	Subject Discontinuation from Study Drug/Device	26
9.2.	Subject Withdrawal from Study	26
9.3.	Study Termination Criteria	26
9.4.	Deviations from the Protocol.....	27
10.	TABLE 2: SCHEDULE OF ASSESSMENTS.....	28
10.1.	Details of Study Assessments	31
10.1.1.	Informed Consent	31
10.1.2.	Medical History	31
10.1.3.	Prior and Concomitant Medications	31
10.1.4.	Physical Examination	31
10.1.5.	Chest Imaging.....	31
10.1.6.	RT-PCR COVID-19 Test	32
10.1.7.	Vital Sign Measurements.....	32

10.1.8.	Respiratory Failure Status.....	32
10.1.9.	12-Lead Electrocardiogram (ECG).....	32
10.1.10.	8-point NIAID Ordinal Scale.....	32
10.1.11.	Pregnancy Test.....	33
10.1.12.	Methemoglobin.....	33
10.1.13.	Laboratory Evaluation	34
10.1.14.	Symptomatic Rebound Testing Post INOpulse Discontinuation.....	34
10.1.15.	Adverse Events	34
10.1.16.	Drug Dispensing – Treatment Period	35

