8.1 Sample Size Considerations

Initial assessment of the sample size is based on the historical experience of ~30% of hospitalized COVID-19 subjects deteriorating to needing increased respiratory support and the preliminary experience in the Emergency Expanded Access that indicated ~15% of INOpulse-treated subjects deteriorate.

More recent data suggest that ~15% of hospitalized COVID-19 subjects deteriorate to needing increased respiratory support. We hypothesize that ~6% of iNO-treated subjects deteriorate.

Using 15% for the placebo arm and 6% for the INOpulse arm, a total sample size of 500 subjects yields 93% statistical power for a 1:1 randomized trial with a two-sided p-value of 0.05.

Based on this analysis of the DRF endpoint, we are targeting a sample size of 500 subjects.

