13.0 Statistical Methods

All analyses will use SAS version 9.4 or higher.

Data from all study sites will be pooled for analyses.

Unless otherwise noted, all summaries will be provided by treatment group: INOpulse and placebo. Demographic summaries will also be provided by stratification group (separately for each stratification factor, described in Section 8.2 above) as a subgroup analysis.

Unless otherwise noted, continuous variables will be summarized using number of observations (n), mean, standard deviation (std), median, first quartile (Q1), third quartile (Q3), minimum and maximum values. The minimum and maximum values will be displayed to the same level of precision as the raw data; the mean, median, Q1 and Q3 values to one additional decimal place and the std to two additional decimal places.

Categorical variables will be summarized using counts and percentages. Percentages will be rounded to one decimal place, except 100% will be displayed without any decimal places and percentages will not be displayed for zero counts.

All participants will be used in the analyses, as per the analysis populations described in Section 11.0 above, using all non-missing data available. Missing data in the logistic regression analysis of DFR will be analyzed as follows: If there is missing data for more than 5% of the cases for the outcome variable, a tipping point analysis will be performed. This will be done as a sensitivity analysis to determine whether or not the data is missing at random, and if the data is not missing at random, how robust is the parameter estimate in the model. The MI and MIANALYZE procedures in SAS¹ will be used to perform this analysis.

As a secondary sensitivity analysis, if there is missing data for more than 5% of the subjects at any time point in the NIAID assessments, the MI procedure in SAS will be utilized to impute missing values for NIAID score, and the statistical models will be run again using the imputed data points to compare the validity of the results using MIANALYZE.

1. SAS/STAT 14.2 User Guide. 2016, 6130 – 6135. SAS Institute Inc., Cary, NC.

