13.5.2 Type I Error Rate

A gatekeeping methodology will be utilized for the primary and secondary hypothesis testing.² This gatekeeping method controls the study-wise Type I error rate at 5% associated with the study's primary and secondary endpoint families. If the primary endpoint is found to be statistically significant, the p-value of 5% will be used to test the first of the secondary endpoints. This testing of the secondary endpoints will continue in a hierarchical manner, until one of the statistical tests is not found to be significant. If this occurs, none of the remaining secondary endpoints will be tested. The hierarchy for the secondary endpoints is shown as they are listed in Section 13.5.5. If the primary endpoint is found not to be statistically significant, then the statistical testing of the secondary endpoint family will not be performed.

2. <https://www.fda.gov/regulatory-information/search-fda-guidance-documents/multiple-endpoints-clinical-trials-guidance-industry>

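### The protocol's sample size of 382 does not follow from its printed inputs, which give 322 (348 with continuity correction)

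*Protocol*

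**What the plan says.** Protocol 17.1, under Expected Sample-Size, gives the planning rates ("Using 30% for the placebo arm and 15% for the iNO arm") and says that this "results in a sample size of 382 for a 1:1 randomized trial with 90% power for one-sided p-value of 0.025". The same subsection of the synopsis has the same calculation: "Using 30% for the placebo arm and 15% for the iNO arm results in a sample size of 382". Neither place names a formula, a continuity correction, a dropout allowance or a variance inflation for covariates. Both then set a target of about 500 subjects, citing this calculation as the basis, and add that the number may have to be revisited.

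SAP 8.1 mentions the 30% and 15% as the initial assessment but does not carry over the 382. It moves to new rates: "Using 15% for the placebo arm and 6% for the INOpulse arm, a total sample size of 500 subjects", with power stated "for a 1:1 randomized trial with a two-sided p-value of 0.05". SAP 13.5.3 also uses a two-sided 5% level. SAP 13.5.2 sets a study-wise 5% without giving sidedness.

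**The concern.** The protocol prints every input that a two-proportion sample size needs: both rates, the allocation, the power, the alpha and its sidedness. The total should therefore be reproducible to within the choice of formula. It is not, so n, alpha and power as printed cannot all be right.

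Two things are at stake, both modest. First, 382 is the only quantitative basis the protocol text gives for its target of about 500, and any later re-assessment ought to start from a calculation that can be repeated. Second, if the 382 really came from a stricter alpha than the one printed, the protocol was planned at a level that differs from the two-sided 5% in the SAP, and a reader cannot tell which was intended.

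**Working it through.** **Inputs** (Protocol 17.1 and synopsis): p1 = 0.30, p2 = 0.15, difference d = 0.15, mean rate p̄ = 0.225, 1:1 allocation, power 90% (z = 1.2816), one-sided alpha 0.025 (z = 1.9600, the same critical value as two-sided 0.05).

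**Pooled formula at the printed alpha**

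n per arm = [z_α √(2p̄(1−p̄)) + z_β √(p1(1−p1) + p2(1−p2))]² / d²

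- √(2 × 0.225 × 0.775) = 0.59055
- √(0.21 + 0.1275) = 0.58095
- n = (1.9600 × 0.59055 + 1.2816 × 0.58095)² / 0.0225 = (1.15746 + 0.74451)² / 0.0225 = 160.78, so 161 per arm, **322** in total.

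**Continuity correction**

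n_cc = (n/4) × [1 + √(1 + 4/(n d))]² = 173.86, so 174 per arm, **348** in total.

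**Other methods at the same inputs**

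| Method | n per arm | Total |
|---|---|---|
| Log-odds, variance at the mean rate | 153.07 → 154 | 308 |
| Unpooled variance | 157.61 → 158 | 316 |
| Arcsine | 158.71 → 159 | 318 |
| Pooled (above) | 160.78 → 161 | 322 |
| Pooled variance under both hypotheses | 162.87 → 163 | 326 |
| Wald log-odds | 168.23 → 169 | 338 |
| Fisher's exact (power 0.9004) | 172 | 344 |
| Continuity-corrected | 173.86 → 174 | 348 |
| Log relative risk | 174.96 → 175 | 350 |

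The highest total is 350, which is 32 below the stated 382. The formula that SAP 13.5.3 cites for logistic regression with a binary covariate gives 322 here, the same as the pooled formula.

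**What does give 382**

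Changing only the alpha to one-sided 0.0125 (z = 2.2414) in the pooled formula:

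n = (2.2414 × 0.59055 + 0.74451)² / 0.0225 = (1.32366 + 0.74451)² / 0.0225 = 190.10, so 191 per arm, exactly **382**.

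At that alpha, power is 0.8998 with 190 per arm and 0.9015 with 191, so 382 is the smallest equal-arm total that reaches 90%.

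**Could an inflation explain it?**

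- From 322: 1 − 322/382 = 15.7% loss.
- From 348: 1 − 348/382 = 8.9% loss.

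Neither rate is in the documents. The only missing-data percentage they print is in SAP 13.0: "If there is missing data for more than 5% of the cases for the outcome variable, a tipping point analysis will be performed". That triggers a sensitivity analysis and is not a planning allowance. Used as one, 5% gives 322/0.95 = 338.9 (340 in equal arms) or 348/0.95 = 366.3 (368 in equal arms).

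**Power at 382 and one-sided 0.025**

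Pooled formula: z = (0.15 × √191 − 1.9600 × 0.59055) / 0.58095 = 1.576, so power is 94.2%. Other methods give 94.6% (exact power of the chi-square test), 93.2% (Wald log-odds) and 93.0% (Fisher's exact).

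**The case against.** The strongest reply is that the figure no longer does any work. The protocol labels it an initial assessment, warns that it may change and leaves detail to the SAP. SAP 8.1 then drops 382 and supports 500 on 15% versus 6%. Enrolment, the primary test, the futility rule and the final alpha do not depend on 382. The protocol also shows no step from 382 to 500, so putting 322 in its place would leave the target no better or worse supported. All of this stands, and it is why the point is minor. It does not make the figure right: 382 is still in current protocol text in two places, offered as the basis of the target.

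A second reply is that no formula is named, the planned analysis is a covariate-adjusted logistic regression, and an unstated allowance cannot be ruled out. It is true that 322 and 348 are two choices within a range of 308 to 350. But no method tried comes within 30 subjects of 382. The text also says that the two rates, at the stated power and alpha, produce that number, and it mentions no inflation. If one was used, stating it settles the matter.

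The explanation through a halved alpha is an inference. The exact match makes it plausible, and it should stay a hypothesis until the sponsor confirms it.

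**Conclusion.** The stated 382 is wrong as written. On the printed inputs the total is 322, or 348 with continuity correction, so the protocol overstates the requirement by 60 subjects (382/322 = 1.19) or 34 (382/348 = 1.10). Equivalently, 382 subjects would give about 94% power at one-sided 0.025 (93.0% to 94.6% by method), not 90%.

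This rests on taking the printed rates, allocation, power and alpha at face value, with no unstated inflation. The discrepancy is conservative and does not threaten the trial, since about 500 subjects are planned and the SAP now supports that number on other rates. Severity is minor; confidence that the printed inputs do not yield 382 is high.

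**What to change.** Amend the sample-size text in Protocol 17.1 and the synopsis in one of these ways:

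- If an alpha other than one-sided 0.025, or an inflation for loss or covariates, was used to reach 382, state it. If the alpha was one-sided 0.0125, reconcile it with the two-sided 5% in SAP 8.1 and 13.5.3 and the study-wise 5% in SAP 13.5.2.
- Otherwise restate 382 as 322 (or 348, naming the continuity correction), or keep 382 and give its power as about 94%.

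Name the formula in either case. Keep the target of 500. This point asks for no change to the SAP's power statement. The cost is wording in two protocol places, with no change to enrolment or analysis.
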